**A randomized placebo-controlled single center pilot study of the safety and
efficacy of tralokinumab in subjects with moderate to severe alopecia areata**

PI: [name]

NCT02684097

Document date: 8-11-2015

A randomized placebo-controlled single center pilot study of the safety and efficacy of tralokinumab in subjects with moderate to severe alopecia areata

PI: [name]

NCT02684097

Document date: 8-11-2015

A randomized placebo-controlled single center pilot study of the safety and efficacy of tralokinumab in subjects with moderate to severe alopecia areata

Institution:

Icahn School of Medicine at Mount Sinai
Department of Dermatology

[REDACTED], [name]
[name]
[contact]
[contact]

Investigators:

Principal Investigator:
[name], PhD

Co-investigators:
[name]

Protocol Version: April 21, 2015

Amendment # 1: August 11, 2015

Amendment #2: September 30, 2015

HYPOTHESES:

Primary Hypothesis:

1. It is hypothesized that IL-13 is involved in the pathogenesis of alopecia areata (AA).

Secondary Hypothesis:

1. Tralokinumab is superior to placebo for induction of hair regrowth in patients with moderate to severe alopecia areata, and will result in improved clinical outcomes for subjects with concomitant atopic dermatitis (AD).

OBJECTIVES and ENDPOINTS:

Primary objective

- 1) This is a pilot study intended to look at IL-13 associated cellular and molecular markers in the skin of patients with alopecia areata and to gain some insight into whether blocking IL-13 with Tralokinumab will affect those markers and hair regrowth

Secondary objectives

- 1) To study the safety of tralokinumab in patients with moderate to severe alopecia areata.
- 2) Study the safety of tralokinumab in patients with concomitant moderate to severe alopecia areata and atopic dermatitis.
- 3) Study the mechanism of action of tralokinumab in patients with moderate to severe alopecia areata.
- 4) Study the mechanism of action of tralokinumab in patients with concomitant moderate to severe alopecia areata and atopic dermatitis.

Primary endpoints

- 1) Change from baseline in cellular, and molecular markers in skin biopsies after treatment.

Secondary endpoints

- 1) Percentage change from Baseline in the Severity of Alopecia Tool (SALT) at Week 24.
- 2) Percentage of patients achieving 50% or greater improvement in their SALT score (SALT₅₀) at Week 24, compared to Baseline.

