A recent study performed in medical centers across Boston, that included a review of 3568 patients with alopecia areata (over 11 years) found that 38.2% of patients with AA also had atopic dermatitis (AD) and/or other atopic conditions (asthma, allergic rhinitis, etc.), with another 35.9% having contact dermatitis or other types of eczema (which might represent misdiagnosed AD as well).³ The main condition associated with AA was AD. Family or personal history of AD was found to be the number one risk factor for AA. A recent publication showed that patients with AA with concomitant AD show a genomic profile, highlighting a set of genes that overlap with AD (biopsies of AD skin were not available).⁴ These include T-cell related and Th2-pathway related genes that modulate epidermal differentiation and drive abnormal T-cell responses. Furthermore, 5 of the 6 transcriptional “hot spots” found within the AA blood and skin gene expression signatures coincide with regions previously reported to be relevant to atopic dermatitis (AD) susceptibility. It was also shown that FLG mutations are significantly associated with the presence of AD among AA patients, and with a more severe clinical presentation of AA.⁴ These data support evidence of a shared genetic background and pathophysiology for patients with AA and AD.

Preliminary analyses from our laboratory (Fig. 1) showed an elevation of IL-13 mRNA expression by RT PCR. However, in order to correctly characterize the overall inflammatory networks in AA and to evaluate how they relate to those in AD, a much larger sample size is needed. In addition to the clinical reversal of the alopecia, we need to also evaluate the tissues effects of Th2/IL-13 antagonism and changes in the immune and cellular markers in affected skin.

Figure 1

[figure not shown]

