Fig 1. Figure 1 shows comparable cytokine expression of the defining Th2 cytokine/IL-13, the defining Th1 cytokine/IFN gamma, and the Th17/IL-23 cytokines/IL-17A and IL12/23p40 in AA and AD. Lesional psoriasis skin tissues show a significantly higher expression of both IL-17A and IFN gamma, with significantly lower expression of IL-13 as compared with both AA and AD. Significant decreases in mRNA expression of IL-13, and IL12/23p40 are seen after treatment with intralesional corticosteroids, without significant changes in the other cytokines. P value= 0.0002 for the IL-13, and p=0.1 for the IFN gamma lesional vs non-lesional alopecia skin comparisons. JAK3 shows similar activation in AA, AD, and Psoriasis. NL- non lesional skin from scalp of AA patients; L- lesional skin from scalp of AA patients; PTX- post intralesional steroid treatment skin from scalp of AA patients; PS-psoriasis lesional skin; AD- AD lesional skin. N=6 patients for both NL and L, and 4 for PTX.

STUDY DESIGN:

This is a randomized, double-blind, placebo-controlled pilot study of a total of 30 subjects with moderate to severe alopecia areata involving 30-100% of the scalp. We expect 50% of these subjects to have concomitant alopecia areata (AA) and atopic dermatitis (AD).

Subjects with AA alone (15 subjects) will be randomized (2:1) to either receive tralokinumab 300 mg (150 mg/ml) or placebo via subcutaneous injection using 2 pre-filled syringes Q2W for 24 weeks. Subjects with concomitant alopecia areata and atopic dermatitis (15 subjects) will be randomized separately in a 2:1 ratio to receive tralokinumab 300 mg (150 mg/ml) or placebo via subcutaneous injection using 2 pre-filled syringes Q2W for 24 weeks.

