Subjects with concomitant AD will have two additional skin biopsies at Baseline (one from involved skin and one from uninvolved skin), and one additional biopsy at Week 24 or Early Termination visit (in the vicinity of the involved area biopsied at Baseline). An optional biopsy will be performed at Week 12, close to the area that was involved and biopsied at Baseline. All biopsies will be 4.5 mm in diameter.

Our experience in AD¹²⁻¹⁴, and past experience in psoriasis^{15, 16} showed that biomarker studies in skin tissues are critical to the understanding of key pathogenic pathways that are upregulated in each disease and how well they are suppressed with effective treatment. These mechanistic studies coupled with clinical trials are key in the disease to shed light on important disease mechanisms, and to explain which molecules are suppressed by each therapeutic target. We now have data that shows that IL-13 is significantly upregulated in both AD and AA lesions compared to nonlesional skin. It is very important to associate the clinical responses with suppression of this cytokine and related molecules as well as other pathway cytokines in skin tissues. Both the whole genomic profiling and individual molecular and cellular markers are very important in order to understand how well anti-IL-13 will change/suppress AA-associated pathways and compare with those that will be suppressed in AD.

At Baseline, serum will be obtained for DNA (1 PaxGene), RNA (2 PaxGene), and proteomic analysis (2 tubes serum). Studies of RNA and proteomic analysis will further be performed at Weeks 12 and 24. Serum levels of various biomarkers such as interferon gamma, IL-2, IL-12, IL-13, IL-17A, IL-5, IL-10, IL-31 and IL-4 have been shown to be elevated in patients with alopecia areata. Therefore we will assess these Th1, including interferon gamma, Th2, Th17, and Th22 markers in serum before and after tralokinumab treatment. Measurements of serum anti-drug antibodies (ADA) including neutralizing antibodies (nAb), as well as serum tralokinumab levels will be performed at Baseline, Weeks 4, 12, and 24 and at Early Termination visit if it occurs prior to Week 24.

Mechanistic blood analyses including RNA, DNA, and proteomic analysis, as well as ADA and serum drug levels will be conducted collaboratively with Medimmune/Astra Zeneca.

INCLUSION CRITERIA:

1. Male or female, aged from 18 to 75 years, inclusively at the time of signing the informed consent document.

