The Principal Investigator will provide safety data to an independent Data and Safety Monitoring Board every 12 months. This DSMB will be comprised of board certified dermatologists who are not directly related to this study. The DSMB will review the data and provide a report of their findings to the Principal Investigator.

EARLY TERMINATION

Any individual whose health or well being may be threatened by continuation in this study will be discontinued by the investigator.

If a female subject becomes pregnant at anytime during the study, she will be discontinued immediately. She will be asked to provide the investigator with medical updates throughout her pregnancy and on the final outcome of the pregnancy.

Any subject who chooses to discontinue the study, or is discontinued from the study by the investigator will be asked to return for a final Early Termination visit for the procedures listed in the Schedule of Events table.

Considering there is no current treatment that is very effective in treating alopecia areata, these subjects are highly motivated to participate in any study that may provide a treatment option. Thus, we have accounted for a 10% drop out rate, and plan to enroll 30 subjects in order to have 27 subjects complete the study.

INVESTIGATIONAL DRUG SUPPLY

In this double-blind study, the investigator will supply tralokinumab (formulated at 150 mg/ml in an isotonic sodium acetate buffer at pH 5.5 in accessorized prefilled syringes for subcutaneous injection) 300 mg for up to 20 subjects and placebo for up to 10 subjects. The tralokinumab and placebo will be provided by MedImmune as 150 mg tralokinumab (and matching placebo) prefilled syringes. Both the 150 mg tralokinumab and the matching placebo prefilled syringes will be of the same quality and identical in size and shape. All study medication will be stored in a secure cool area between 2-8°C. Study drug will be administered to subjects at each visit, and any unused study drug will be kept at the study site. The number of missed doses will be documented for each subject. The investigative site will account for all study drug dispensed and stored during the study.

EFFICACY EVALUATIONS

The following efficacy parameters will be obtained at the previously specified visits:

1. Investigator evaluation of alopecia on the scalp (efficacy of the drug) using the following tools:

Severity Alopecia Tool (SALT)⁵ score:

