Prior to beginning this study, approval for all study related documents (protocol, consent form, advertising) would be obtained from the Icahn School of Medicine at Mount Sinai Program for the Protection of Human Subjects (Institutional Review Board), [name].

DATA ANALYSES:

This is an exploratory study therefore sample size has been kept relatively low. Data collected from this study will be used to obtain estimates of differences and variability, of the change in treatment for IL-13. If the variability of the Post vs Pre differences are of the magnitude of the LS vs NL differences observed in preliminary data (SE=0.46) then the size of the confidence interval in differences could be observed in this study would be 0.58. As for the secondary outcome, the spontaneous regrowth rate in alopecia areata is 4%. To demonstrate efficacy of the study drug, a response rate of at least 50% is required. To be statistically significant, we would require a minimum of 10 subjects in the study, with an expected response rate of 0 or 1 subject in the placebo group.

MECHANISTIC STUDIES DATA ANALYSES:

For the comparisons of expression levels of lesional, and non-lesional AA skin, we will use RT-PCR, and gene-arrays. RT-PCR values will be normalized to the housekeeping gene hARP (validated in all our AD studies) and log2-transformed prior to analysis. Microarray data will be preprocessed using standard pipeline (exhaustively used by our group in a large number of studies) and log-2 transformed expressions. Adjustments by batch effect and clinical variables will be carried out if needed using ComBat. Mixed effect model on R's *limma* framework will be used and p-values for the moderated t-tests and paired-t-test will be adjusted by Benjamini-Hochberg procedure.

Extensive bioinformatics tools will be employed to gain insights on the results and test hypotheses that are generated in the "data mining stage". This will include (but is not be limited to) pathway and gene-set enrichment analyses using Ingenuity software, GSEA, the R package GSVA (Gene Set Variation Analysis) and other in-house codes produced by our group.

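### AA-alone and AA+AD subjects are randomized separately and have separate mechanism objectives, but the stated analysis has no randomization-group term and no by-group estimate

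*Combined protocol and SAP*

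**What the plan says.** STUDY DESIGN plans 30 subjects, about half of them with AD. The 15 with AA alone are randomized 2:1 to tralokinumab or placebo. For the others, "Subjects with concomitant alopecia areata and atopic dermatitis (15 subjects) will be randomized separately in a 2:1 ratio".

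Under OBJECTIVES and ENDPOINTS, secondary objective 3 concerns mechanism in AA. Objective 4 is its counterpart: "Study the mechanism of action of tralokinumab in patients with concomitant moderate to severe alopecia areata and atopic dermatitis". The primary endpoint is the change in cellular and molecular markers in skin biopsies. It names neither the tissue (scalp or AD skin) nor the group.

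The protocol gives reasons for keeping the groups apart. STUDY DESIGN says that "IL-13 is significantly upregulated in both AD and AA lesions compared to nonlesional skin", and sets out to compare the pathways suppressed in AA with those suppressed in AD. The INTRODUCTION reports that "FLG mutations are significantly associated with the presence of AD among AA patients, and with a more severe clinical presentation of AA", and that patients with both conditions show a genomic profile that includes Th2-related genes overlapping with AD.

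DATA ANALYSES and MECHANISTIC STUDIES DATA ANALYSES contain the statistical methods. Neither names the AA-alone and AA+AD groups. The nearest provision is general: "Adjustments by batch effect and clinical variables will be carried out if needed using ComBat".

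**The concern.** The design separates the two groups at randomization and the analysis does not take this up. Two things are at stake.

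- **Precision.** If mean change differs between the groups, a model without the group term puts that difference into the residual. The interval is then wider than it need be and power is lost, in a trial of only 30 subjects.
- **Interpretation.** The primary hypothesis is that IL-13 is involved in AA. A pooled drug effect averages the AA-alone and AA+AD effects, so it can be positive when only one group responds. Without by-group estimates the report could not show this, and objectives 3 and 4 have no stated method that tells the groups apart.

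**Working it through.** **The plan's own figures.** EARLY TERMINATION plans for 10% dropout: "plan to enroll 30 subjects in order to have 27 subjects complete the study". This reproduces, since 27/0.9 = 30. DATA ANALYSES gives one confidence-interval size, 0.58, from SE = 0.46, without stating n, confidence level, half or full width, or group. At 95% it does not reproduce from a planned sample size. The nearest results include 0.570 (full width, normal quantile, n = 10, SD 0.46) and 0.560 (half-width, t, n = 18, SD 1.127). Nothing below depends on 0.58.

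**Inputs.** Allocation is 10:5 in each group (STUDY DESIGN). The 95% level, two-sided, is my assumption. The SD of change is either 0.46, or, if 0.46 is the standard error of six paired differences (Figure 1 legend), 0.46 × √6 = 1.127. Log2 units are assumed from MECHANISTIC STUDIES DATA ANALYSES. The group difference in mean change, d in within-group SD units, is not in the documents, so a range is used.

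**Effect of omitting the group.** With 15 subjects per group, a difference d adds 30 × d²/4 = 7.5d² to the residual sum of squares (in units of the within-group variance). The ratio of half-widths, without the term to with it, is about

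(t₂₈/t₂₇) × √[(28 + 7.5d²)/28], with t₂₈ = 2.048 and t₂₇ = 2.052.

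For d = 1 this is 0.998 × √(35.5/28) = 1.124. Type I error and power come from simulating 10:5 in each group (at least 40,000 trials per case), with a true effect of 1.1 SD for power.

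| d | CI too wide by | Type I error, no term | Power, no term | Power, with term |
|---|---|---|---|---|
| 0 | 0% | 5.0% | 78% | 78% |
| 0.5 | 3% | 4.4% | 76% | 78% |
| 1 | 12% | 2.9% | 70% | 78% |
| 1.5 | 26% (formula), 27% (simulation) | 1.4% | 60% | 78% |

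**Effect in one group only.** Take 2 SD in AA+AD, zero in AA alone, and no difference between the placebo groups. The pooled effect is (2 + 0)/2 = 1.0 SD. By simulation it is significant in about 47% of trials without the group term and 62% with it. The term sharpens the pooled test but does not show where the effect lies.

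**By-group precision (95% half-widths).**

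- One group, 10:5: t₁₃ × SD × √(1/10 + 1/5) = 2.160 × 1.127 × 0.548 = 1.33 (0.54 if SD = 0.46).
- Pooled with group term, 20:10: t₂₇ × SD × √(1/20 + 1/10) = 2.052 × 1.127 × 0.387 = 0.90 (0.37 if SD = 0.46).
- Difference between the group effects: t₂₆ × SD × √(0.1 + 0.2 + 0.1 + 0.2) = 2.056 × 1.127 × 0.775 = 1.79 (0.73 if SD = 0.46).

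**The case against.** Several stronger readings are tempting, and the documents do not support them.

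- **The intervals are definitely too wide.** A reader might infer this from raised IL-13 in both diseases or from the filaggrin finding. Those statements concern expression level and severity at presentation, not change on treatment. The endpoint is a change from baseline, so an additive difference in level cancels. Figure 1 reports comparable IL-13 in AA and AD. The loss is conditional, and where it occurs the test errs on the conservative side.
- **The primary result mixes two diseases.** Every subject has AA, and scalp is biopsied in everyone. AD-skin biopsies are additional, separate specimens. A fall in scalp IL-13 in an AA+AD subject is still an observation in AA tissue. Mixing would arise only if AD-skin samples were pooled into the primary endpoint, which the text neither says nor excludes. Nor is the pooled contrast confounded by AD, because allocation is 2:1 in both groups.
- **Nothing in the plan uses the groups.** SCORAD, EASI and IGA are confined to AA+AD subjects, and the intent to compare AA with AD is stated. What is missing is a statistical method.
- **ComBat will remove AD status.** AD is not listed among the variables to be adjusted, and clinical variables can be kept as preserved covariates. This is a risk to close off, not a planned error.

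It is also fair to say that by-group results in a 30-subject pilot will be weak: in AA alone, power for a 1.1 SD effect is about 46%. A stratified SALT50 test would add little with the 0 or 1 placebo responder that the plan expects.

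What stands is that the stated methods omit the randomization group. The genomic rationale in the INTRODUCTION makes a different response to IL-13 blockade plausible, and a difference in response does not cancel in a change score.

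**Conclusion.** The point holds as an omission from the stated methods. It does not make the analysis invalid. The unstratified test keeps its error rate and may lose power: none at d = 0, and up to 18 percentage points (78% to 60%) at d = 1.5. These sizes rest on assumed group differences, equal within-group SDs, and all 30 subjects analysed in exact 10:5 splits.

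Interpretation matters more than precision. A pooled effect is a valid average over the enrolled population, but it cannot by itself support a statement about AA without AD. The 47% and 62% figures illustrate this for one assumed pattern of effects and are not a forecast.

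The change is worth making before unblinding, because choosing afterwards whether to split or adjust by AD status would be open to the charge of selection.

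**What to change.** Amend DATA ANALYSES and MECHANISTIC STUDIES DATA ANALYSES to say that:

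1. The randomization group (AA alone or AA+AD) is a fixed factor in every drug-versus-placebo model of skin-marker change, including the limma design matrix and the IL-13 model, and in the models for change in SALT, AASIS and AA-QoL.
2. Scalp and AD-skin specimens are analysed separately, and the tissue for the primary endpoint is named.
3. Drug-minus-placebo estimates with confidence intervals are reported for AA alone, for AA+AD, and for their difference, and labelled descriptive. For SALT50, responder counts by group and arm are enough.
4. The conclusion about IL-13 in AA is read alongside the AA-alone estimate and does not rest on the pooled one only.
5. If ComBat is used, AD status is a preserved covariate and not a batch.

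The cost is wording and one degree of freedom (28 to 27), which is negligible: the half-width at d = 0 rises by about 0.2%. By-group intervals will be wide, about ±1.33 log2 per group against ±0.90 pooled if the SD is 1.13, and should not be presented as tests.

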After providing informed consent, subjects will be assessed for study eligibility at the Screening visit (day -28 to day -1), which includes: limited physical examination (including vital signs); assessment of regrowth pattern; SALT scoring; electrocardiogram (ECG); review of medical history and concomitant medications as well as prior medications/treatments; and serum pregnancy test (if applicable). Laboratory tests will be performed for Complete Blood Count (CBC with differentials (basophils, eosinophils, lymphocytes, monocytes, neutrophils), serum chemistry (albumin, alanine aminotransferase (ALT), alkaline phosphatase (ALP), aspartate aminotransferase (AST), creatinine, potassium, sodium and total bilirubin), as well as hepatitis B surface antigen (HbsAg), hepatitis C antibody, and undergo testing for human immunodeficiency virus (HIV). Subjects will also undergo tuberculin purified protein derivative (PPD) or QuantiFERON TB-Gold test (QFT) testing.

Subjects who meet eligibility criteria (meeting all inclusion and exclusion criteria) will undergo Baseline / Day 0 assessments. These assessments include vital signs, assessment of regrowth pattern, SALT scoring, questionnaires (AASIS and AA-QoL), clinical photography, urine pregnancy test (if applicable), and blood collection for chemistry, hematology, mechanistic studies, DNA analysis, RNA analysis, proteomic analysis, anti-drug antibody (ADA) measurement, and serum tralokinumab levels. In addition, SCORAD, EASI and IGA scores will be performed in subjects with AD only. Two scalp biopsies will be obtained (one from an involved area of the scalp and one from an uninvolved area). Subjects with concomitant AD will have two additional skin biopsies (one from involved skin and one from uninvolved skin). Concomitant medications and any adverse events will be assessed.

Subjects will then undergo randomization, and will receive the first dose (300 mg SC) of study drug (tralokinumab or placebo). Subjects will continue to receive bi-weekly injections of study drug (300 mg tralokinumab or placebo) through Week 24.

Subjects will return for visits every two weeks to have the following performed: vital signs will be taken prior to every study drug administration; concomitant medications and any adverse events will be assessed; and a urine pregnancy test will be performed (if applicable).

For the first four doses of Investigational Product (IP), subjects will be monitored after IP

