9. Subject is judged to be in good general health as determined by the principal investigator based upon the results of medical history, laboratory profile, and physical examination performed at Screening.
10. Subjects may be naïve to treatment or unresponsive to intralesional steroids or other treatments for alopecia areata.

EXCLUSION CRITERIA:

Subjects should not enter the study if any of the following exclusion criteria are fulfilled:

1. History of male or female pattern hair loss Ludwig stage III or Hamilton > stage V.
2. Subjects in whom the diagnosis of alopecia areata is in question.
3. Any disorder, including but not limited to, cardiovascular, gastrointestinal, hepatic, renal, neurological, musculoskeletal, infectious, endocrine, metabolic, haematological, psychiatric, or major physical impairment that is not stable in the opinion of the Investigator and could:
 - Affect the safety of the subject throughout the study
 - Influence the findings of the studies or their interpretations
 - Impede the subject's ability to complete the entire duration of study
4. Known history of allergy or reaction to any component of the IP formulation.
5. History of anaphylaxis following any biologic therapy.
6. The following treatments within 4 weeks before the Baseline visit, or any condition that, in the opinion of the investigator, will likely require such treatment(s) at any time during the study:
 - Systemic corticosteroids
 - Immunosuppressive/immunomodulating drugs (eg, cyclosporine, mycophenolate-mofetil, IFN- γ , Janus kinase (JAK) inhibitors, azathioprine or methotrexate), Ultra-Violet (UV) B phototherapy; and/or Psoralen Ultra-Violet A (PUVA) therapy.
7. Treatment with topical corticosteroids, tacrolimus and/or pimecrolimus within 1 week before the Baseline visit.
8. Subject has taken enzyme-modifying drugs that are moderate inhibitors/potent inducers of cytochrome P450 3A4 or potent inhibitors of cytochrome P450 2C19

enzymes (such as cimetidine, quinidine, erythromycin, ciprofloxacin, fluconazole, ketoconazole etc...) and strong inducers of CYP enzymes (such as rifampin etc...), in the previous 28 days before day 0.

9. A helminth parasitic infection diagnosed within 6 months prior to the date informed consent or assent obtained that has not been treated with, or has failed to respond to, standard of care therapy.

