10. History of clinically significant infection, including acute upper or lower respiratory infections, requiring antibiotics or antiviral medication within 30 days prior to the date informed consent or assent is obtained or during the run-in period.
11. Tuberculosis requiring treatment within the 12 months prior to enrolment (Visit 1).
12. Any clinically significant abnormal findings in physical examination, vital signs, ECG, hematology, clinical chemistry, or urinalysis during the run-in period, which in the opinion of the Investigator, may put the subject at risk because of his/her participation in the study, or may influence the results of the study, or the subject's ability to complete entire duration of the study.
13. History of chronic alcohol or drug abuse within 12 months of the enrolment visit, or a condition associated with poor compliance as judged by the Investigator.
14. Positive hepatitis B surface antigen or hepatitis C virus antibody serology. Subjects with a history of hepatitis B vaccination without a history of hepatitis B are allowed to be enrolled.
15. History of any known primary immunodeficiency disorder including a positive human immunodeficiency virus (HIV) test at enrolment, or the subject taking antiretroviral medications as determined by medical history and/or subject's verbal report.
16. Current tobacco smoking (smoking must have stopped for \geq 3 months prior to enrollment) or a history of tobacco smoking for \geq 10 pack-years (one pack year = 20 cigarettes smoked per day for 1 year).
17. History of cancer:
 - a. Subjects who have had basal cell carcinoma, localized squamous cell carcinoma of the skin or in situ carcinoma of the cervix are eligible provided that the subject is in remission and curative therapy was completed at least 12 months prior to the date informed consent was obtained
 - b. Subjects who have had other malignancies are eligible provided that the subject is in remission and curative therapy was completed at least 5 years prior to the date informed consent was obtained
18. Use of immunosuppressive medication (including but not limited to: methotrexate, troleandomycin, cyclosporine, azathioprine, systemic corticosteroids including regular treatment with OCS or intramuscular long-acting

depot corticosteroids, or any experimental anti-inflammatory therapy) within 3 months prior to the date informed consent or assent is obtained.

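### No washout is set for intralesional scalp corticosteroids before the Baseline biopsy, although the plan admits subjects who have failed them

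*Combined protocol and SAP*

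**What the plan says.** All references are to the combined protocol and SAP.

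- **Who may enter.** INCLUSION CRITERIA 10 accepts treatment-naive subjects and those "unresponsive to intralesional steroids or other treatments for alopecia areata". It gives no interval since the last treatment.
- **Systemic steroids.** EXCLUSION CRITERIA 6 opens with "The following treatments within 4 weeks before the Baseline visit" and lists systemic corticosteroids, then an open class beginning "Immunosuppressive/immunomodulating drugs (eg, cyclosporine, mycophenolate-mofetil". EXCLUSION CRITERIA 18 bars immunosuppressive medication in the 3 months before consent. Its list is also open, and its steroid entry reads "systemic corticosteroids including regular treatment with OCS or intramuscular long-acting" depot forms.
- **Topical steroids.** EXCLUSION CRITERIA 7 reads "Treatment with topical corticosteroids, tacrolimus and/or pimecrolimus within 1 week before the Baseline visit".
- **Other alopecia treatment.** STUDY DESIGN bars it for as long as a subject takes part in the study. Screening falls 1 to 28 days before Baseline and includes "review of medical history and concomitant medications as well as prior medications/treatments".
- **Biopsies.** The two Baseline scalp biopsies are "one from an involved area of the scalp and one from an uninvolved area". The Week 24 biopsy is taken near the involved Baseline site. The primary endpoint is the change from baseline in cellular and molecular markers in these biopsies.
- **Known effect of the injections.** The Fig 1 legend reports significantly lower IL-13 and IL12/23p40 mRNA in scalp skin after intralesional corticosteroids, with 4 post-treatment patients.

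**The concern.** The protocol controls prior steroid exposure route by route, but omits the one steroid route that its inclusion criteria name. A subject still receiving a failing course of scalp injections can therefore qualify, and the Baseline biopsy may come from recently injected scalp.

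The protocol's own preliminary data link these injections to lower expression of IL-13, the cytokine the study drug blocks. If the Baseline value is already suppressed and recovers by Week 24, the paired change is pushed upward and a fall caused by tralokinumab is partly hidden. The planned lesional versus non-lesional comparison and the planned correlation of expression changes with clinical response use the same measurements.

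**Working it through.** This is mainly a check of wording. The plan gives no figure on this point to reproduce.

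**Step 1. Minimum time off each steroid route before Baseline, as written**

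- Topical: 1 week (exclusion 7).
- Systemic: 4 weeks before Baseline (exclusion 6), and 3 months before consent (exclusion 18).
- Intralesional: none stated. The route appears only in the INTRODUCTION text, the Fig 1 legend and inclusion 10, and none of these sets an interval. Exclusion 19 mentions oral steroids, but only for asthma exacerbations.

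**Step 2. What the on-study ban adds**

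Let *s* be the number of days from Screening to Baseline, from 1 to 28. If participation is taken to start at Screening, the ban gives at least *s* days off injections. The guarantee is the minimum over subjects, which is 1 day. If participation is taken to start later, no interval is guaranteed. The protocol does not say which applies.

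**Step 3. How a recent injection would enter the endpoint**

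On the log2 scale, let *B* be the untreated Baseline value at the involved site, *t* the true change by Week 24, *d* the suppression still present at Baseline and *e* the suppression left at Week 24.

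- Observed change = (*B* + *t* − *e*) − (*B* − *d*) = *t* + (*d* − *e*).
- With recovery, *d* exceeds *e*, so a true fall looks smaller. Without recovery, *d* = *e* and there is no distortion.
- Between arms, the mean of (*d* − *e*) is the same in expectation under randomisation, provided recovery does not depend on the arm. It then cancels, leaving extra variance and possible chance imbalance in arms of about 20 and 10.
- Lesional minus non-lesional at Baseline is shifted by −(*d* at the involved site − *d* at the uninvolved site). If injections go mainly to involved scalp, which is an assumption, the contrast shrinks.

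The documents give no value for *d* or *e* and no number of affected subjects, so no size can be put on any of these terms.

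**Step 4. Delay caused by a 28-day rule**

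For a subject last injected on the day of Screening, added wait = 28 − *s*:

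- *s* = 1: 27 days
- *s* = 14: 14 days
- *s* = 28: 0 days

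**The case against.** The case for leaving the text alone is substantial.

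- **Several things must coincide.** The subject must have been injected shortly before Baseline, the 4.5 mm biopsy must fall on injected scalp, IL-13 must be suppressed despite clinical non-response, and it must recover by Week 24. The documents show none of these for enrolled subjects.
- **Few subjects may qualify.** The INTRODUCTION reserves intralesional steroids for limited involvement, whereas inclusion 5 requires at least 30% scalp hair loss.
- **Fig 1 may not carry over.** It has 4 post-treatment patients and gives neither the injection-to-biopsy interval nor responder status. Inclusion 10 concerns non-responders, and inclusion 6 (no regrowth) removes visible responders.
- **There is a randomised placebo group.** The Post vs Pre sentence in DATA ANALYSES concerns variability and interval width. It does not say that conclusions will rest on uncontrolled within-arm change.
- **Treatment history is reviewed.** Exclusions 6, 7 and 18 can hardly be applied without treatment dates, so the date of the last injection is probably collected already. The analysis also allows adjustment for clinical variables if needed.

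All of this stands as a limit on weight, but it does not close the gap. The open lists in exclusions 6 and 18 could be stretched to cover scalp injections. That is the weaker reading, because both restrict corticosteroids to systemic use and topical steroids needed their own rule. Inclusion 6 screens for hair, not for molecular suppression. Adjustment requires knowing which sites were injected, and nothing in the protocol asks for that.

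A reader might also infer a gap for contact immunotherapy (diphenycyprone, squaric acid dibutyl). The documents do not support that: it is not named, but the immunomodulating class in exclusion 6 plausibly covers it.

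**Conclusion.** The omission is real. As written, the plan permits a Baseline scalp biopsy from a recently injected site, with at most a 1-day guaranteed interval, and that guarantee depends on participation starting at Screening. The possible consequences are a masked within-arm fall, a blurred lesional versus non-lesional comparison, a noisier correlation with clinical response, and noise or chance imbalance between small arms.

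Two stronger readings should be resisted.

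- A reader might infer that the tralokinumab versus placebo comparison of the primary endpoint is biased. The documents do not support this: the expected shift cancels between randomised arms, and neither the number of affected subjects nor the depth or duration of suppression is given.
- A reader might take one subject's share of an arm mean (1/20 on drug, 1/10 on placebo) as the size of the problem. That is the weight of any subject with any deviation, and it does not measure this bias.

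The size of the bias is unknown. The point rests on injections suppressing markers in at least some non-responders, which Fig 1 makes plausible but does not show. This is a cheap improvement of low priority in a 30-subject exploratory pilot.

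**What to change.** 1. Extend exclusion 7 with a clause such as: *or intralesional corticosteroids to the scalp in the 4 weeks before Baseline*. Four weeks matches exclusion 6. The exact length is a clinical choice, because the documents give no duration of effect for this route.
2. In STUDY DESIGN and BIOPSY SPECIMENS, ask that both Baseline scalp biopsies come from scalp not recently injected, where possible.
3. Record the date and site of the last scalp injection. The date is probably collected already, so the site is the likely addition.

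Exclusions 6 and 18 need no change.

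The cost is one amendment to eligibility and biopsy-site wording and, at most, one extra case report form entry. A few candidates would wait up to about 4 weeks. For someone last injected on the day of Screening the wait is at most 27 days, which moves Baseline to 28 days after Screening and so stays within the existing Screening window.
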